**NOTE:** The protocol should describe your research procedures and participant population in detail. Your consent documents, data collection instruments (surveys, questionnaires, interview guides, etc.), and recruitment materials need to be submitted for review as well and should not be attached or incorporated into this protocol document.

### **TIPS ON COMPLETING THE PROTOCOL FORM:**

- If any sections are not applicable to your research, mark that section as N/A (for not applicable)
- Keep an electronic copy of your protocol. If you submit modifications to your study at a later time, you will need to include tracked changes to all affected study documents, including the protocol.
- As you write this protocol, remove the **text boxes** and all instructional text contained inside the text boxes in each section. There should be no **text boxes** or instructional text (including these instructions) in the final version of your protocol.

## 1.0 Purpose of the study:

Charles River Analytics and our collaborators at The New England Consortium propose to develop and evaluate an Immersive Modular Preparedness Intelligent Tutor (IMPRINT). IMPRINT aims to enhance trainee performance and set operational expectations outside of the hot zone in hyper-realistic exercises that challenge physical, psychological, and cognitive capabilities through adaptive behavioral science enhanced virtual reality (VR) modules and seamlessly integrate with HAZWOPER training. The overall objective of IMPRINT Phase II is to conduct a 1-year randomized-controlled trial among regular HAZWOPER Trainees comparing protocol adherence during required hands-on field exercises for trainees who used the IMPRINT behavioral science VR training with trainees who received standard PowerPoint and video training.

We anticipate trainees and classes assigned to the intervention will perform better than those who use standard paper and PowerPoint based activities. We believe their comprehension of topics will be greater, and it is likely that they will have a greater ability to recall HAZWOPER guidelines in the field. We also anticipate after class survey results will indicate a better HAZWOPER training experience and increased levels of satisfaction with the course.

Additionally, we anticipate that trainers using the IMPRINT VR modules will find the tool more effective and engaging compared to standard PowerPoint and video-based training methods. We expect that trainers will report greater ease in delivering complex HAZWOPER concepts and that the VR modules will enhance their ability to facilitate trainee comprehension and recall of HAZWOPER guidelines. We also anticipate that trainer feedback will reflect a more positive teaching experience and higher levels of satisfaction with the training process.

Long-term benefits of participation include improvement in retention of HAZWOPER guidelines when responding to Hazardous Material (HAZMAT) disasters. We anticipate trainees and classes assigned to the intervention will perform better than those who use standard paper and PowerPoint based activities. We believe their comprehension of topics will be greater, and it is likely that they will have a greater ability to recall HAZWOPER guidelines in the field. We also anticipate after class survey results will indicate a better HAZWOPER training experience and increased levels of satisfaction with the course.

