## **8.0 Procedures Involved:**

The standard TNEC 40-hour workbook will be used in both the intervention and control classes.

In the intervention, trainees will be provided with an Oculus VR headset to complete virtual reality modules based on activities covered in the TNEC 40 hour course workbook. In control classes, trainees will complete all of the activities following standard practice which includes filling out sheets, reviewing 2D photographs, and reviewing slides. VR modules will last no longer than 1-5 minutes in length, which is a comparable length to the time allowed for students in control classes to complete their assigned tasks. There will be no differences in content provided between cases and controls. We are examining the effect of a difference in delivery mechanism and interaction with the content to enhance retention, understanding, and performance.

VR modules will be provided intermittently throughout the 40 hour course. Each course is required to be 40 hours in length by the OSHA standard.

All evaluations and assessments of trainees will take place at the same sequence between cases and controls.

Outcomes measured include student accuracy on the TNEC HAZWOPER performance instruments including; 1) the 40 Hr HazWoper Course Workbook, 2) the Toxic Properties Activity, 3) The New England Consortium Health and Safety Training Survey, 4) System Usability Scale (SUS), 5) Occupational Self-

Efficacy Scale - Short Form (OSS-6), 6) iGroup Presence Questionnaire (IPQ), 7) Flow State Scale (FSS), 8) UX for VR Questionnaire, and 9) NASA-TLX

We will first run a two-month pilot to estimate ICC, the intraclass correlation coefficient. We will use ICC to determine effect size for the following 12-month study (see Figure 10). Using this calculation, we will determine expected effect size from the more extensive 12-month portion of the evaluation effort.

Prior to analysis of the 12-month effort, we will use matching techniques based on trainee and trainer characteristics. We will use pretest matching criteria based on trainee cohort population characteristics and prior knowledge ascertained through pre-HAZWOPER training registration information.

[figure not shown]
[figure not shown]

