We will match cases and controls using Euclidian distance between intervention and control samples rather than propensity score matching to find the best match to mitigate risk of confounding due to low sample size following the guidance of [name] (King, G. and Nielsen, R., 2019. Why propensity scores should not be used for matching. *Political Analysis*, 27(4), pp.435-454.). We will compare how these modules enhance student performance across TNEC HAZWOPER performance instruments including; 1) the 40 Hour HAZWOPER Course Workbook, 2) the Toxic Properties Activity, 3) The New England Consortium Health and Safety Training Survey, 4) System Usability Scale (SUS), 5) Occupational Self-Efficacy Scale - Short Form (OSS-6), 6) iGroup Presence Questionnaire (IPQ), 7) Flow State Scale (FSS), 8) UX for VR Questionnaire, and 9) NASA-TLX

We will compare how these modules enhance performance through a t-test.

[figure not shown]
Intervention VR modules will be based on the existing activities within the 40 Hour HAZWOPER Course Workbook and the field exercise including:

Module 1 Duration: 5 Minutes	Activity 3-A What's on the Site?
------------------------------------	----------------------------------

[figure not shown]
Instrument	
3.1 CHEMICAL HAZARDS - 3 • Pg 4
 
ACTIVITY3-A
 
WHAT'S ON THE SITE?
 
Purpose: To start developing a list of clues that can be used to decide if hazardous chemicals are present on site. To get you thinking about what you need to know in order to work safely on site. To stress the importance of information and knowing where to get it.
 
Task: As a group, answer questions 1-3 using the following information: the site description below, the site map on pg. 5, and the photographs in your site packet. Numbers on the site map correspond to photo numbers. The arrows indicate the direction from which the photo was taken.
 
Site Description: Bright Corporation was a small metal plating company located on a 2 acre site. It operated between 1955 and 1992. The company was engaged in plating and painting of small metal parts. A lead acid battery manufacturer occupied the site between 1992 and 1995. The site has been abandoned for six months.
 
 
1. What clues suggest that chemical hazards may be present?
 
2. What else would you like to know about this site before entering?
 
3. Where would you go for this information?
 

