IMPRINT Intervention (Virtual Environment)	

[figure not shown]
Control Part A	
Control Part B	
Module 2 Duration 5 Minutes	Activity 11-A Controlling the Site

Instrument	
DANGER HAZARDOUS WASTE 3.1 Ch. 11 • Pg 13
 
ACTIVITY 11-A
 
CONTROLLING THE SITE
 
PURPOSE: To review the health & safety issues to be considered when developing a site control program.
 
TASK: You are in charge of buried drum removal at the Bright Corporation site. Contaminants include acids and bases, flammable solvents, chlorinated organic solvents, and metals. Using the site map on page 15 and the job description below, answer the questions on the next page.
 
 
• Drums are being unearthed manually using shovels.
 
• They are removed from the pit using an excavator with a drum grappler attached.
 
• Drums are then moved manually, using drum dollies, to the first staging area for opening and sampling.
 
• They are then moved to final staging area with dollies to await bulking and removal.
 
• Emptied drums are crushed before removal.
 
• The excavation has had problems with water build up. The water is pumped using a gasoline pump to a holding area for testing and later removal.
 
• Workers entering the excavation and workers in the drum opening area are in level B protection. Workers in sampling area in level C. All others in the exclusion zone are in level D protection.
 

IMPRINT Intervention (Virtual Environment)	

Control	 
ACTIVITY 11- A (continued)
 
DANGER HAZARDOUS WASTE
 
3.1 Ch. 11 • Pg 15
 
Site Plan Labels:
 
 
EXCAVATION
 
SPOILS PILE
 
EXCAVATOR w/ SPREADER
 
CHANLINK FENCE
 
EQUIPMENT DECON
 
DRUM CRUSHER
 
PERSONNEL DECON
 
SUPPORT ZONE TRAILER
 
RESERVOIR
 
PUMP
 
BUILDING
 
BUILDING
 
BUILDING
 
PREVAILING WIND
 
W-E
 
N
 
S
 
HOT ZONE
 
WARM ZONE
 
COLD ZONE
 

Module 3 Duration 3 Minutes	Decontamination Line Ordering and Field Exercise

Instrument (field training exercise/ evaluation)
		

IMPRINT Intervention (Virtual Environment)
		

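### The stated objective, protocol adherence in field exercises, is in neither outcome list, is tied to the one stated test only by implication, and no outcome is named primary

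*Combined protocol and SAP*

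**What the plan says.** Section 1.0 states one overall objective: a randomised trial "comparing protocol adherence during required hands-on field exercises for trainees who used the IMPRINT behavioral science VR training" with trainees taught by slides and video.

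Section 8.0 then gives the outcomes. The first list begins "Outcomes measured include student accuracy on the TNEC HAZWOPER performance instruments including; 1) the 40 Hr HazWoper Course Workbook, 2) the Toxic Properties Activity" and continues with the TNEC survey, the System Usability Scale and the self-efficacy scale. It ends "6) iGroup Presence Questionnaire (IPQ), 7) Flow State Scale (FSS), 8) UX for VR Questionnaire, and 9) NASA-TLX". The second list, after the matching paragraph, repeats the same nine items.

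The only hypothesis test follows directly: "We will compare how these modules enhance performance through a t-test". It names no instrument, score or time point.

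Two entries in Section 8.0 bring the field exercise in. The modules are introduced with "Intervention VR modules will be based on the existing activities within the 40 Hour HAZWOPER Course Workbook and the field exercise including", and Module 3, headed "Decontamination Line Ordering and Field Exercise", has an instrument row labelled "Instrument (field training exercise/ evaluation" and a closing bracket. The content of that row is not readable in the public text.

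Section 4.0 allocates whole courses, six per arm. It gives no significance level, power or target effect for any outcome.

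**The concern.** A confirmatory trial needs a fixed line from its question to an outcome and from that outcome to a test. Here the question is behaviour in the field, while the listed outcomes are written course work, a training survey and self-report scales. If the lists govern, the trial can be run and analysed exactly as written without any result on field adherence.

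Because no outcome is ranked first, the headline could be chosen among the listed instruments after the data are seen. A difference in usability or workload could then stand in for the adherence comparison that Section 1.0 promises. The sample size does not settle the matter, since it is not tied to any outcome.

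**Working it through.** **1. The plan's own figure.** Section 4.0 gives 180 to 300 participants for the main evaluation. Twelve courses of 15 to 25 give 12 × 15 = 180 and 12 × 25 = 300, which agrees. This is a head count and not a power calculation, so it does not reveal an implied primary outcome.

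**2. The objective against the outcome lists (Section 8.0, identical in both places).**

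| Listed instrument | Field-exercise adherence? |
|---|---|
| 1. Course workbook | No; Section 8.0 names workbook and field exercise as separate sources of the modules |
| 2. Toxic Properties Activity | No |
| 3. TNEC Health and Safety Training Survey | No |
| 4. System Usability Scale | No |
| 5. Occupational self-efficacy short form | No |
| 6. Presence questionnaire | No |
| 7. Flow State Scale | No |
| 8. UX for VR | No |
| 9. NASA-TLX | No |

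Count: 0 of 9 is field-exercise adherence, and 0 is named primary in the readable text.

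**3. The objective against the test.** The sentence before the t-test speaks of performance across the nine instruments. The t-test sentence itself speaks of the modules, and Module 3 has a field evaluation as its instrument. So there are two routes from the test to an outcome: one leads to the nine instruments, the other partly to the field exercise. The text does not choose between them.

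**4. Illustration of leaving the primary open.** The documents give no significance level, number of tests or correlation. I assume two-sided 0.05 per test. For k independent tests the chance of at least one false positive is 1 − 0.95^k, so 1 − 0.95^9 = 0.370. For equally correlated normal test statistics I used numerical integration.

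| Tests | Independent | Correlation 0.5 | 0.7 | 0.9 |
|---|---|---|---|---|
| 9 (all) | 37% | 27% | 20% | 12% |
| 6 (without presence, usability and UX for VR) | 26% | 21% | 16% | 11% |
| 2 (workbook, Toxic Properties Activity) | 10% | 9% | 8% | 7% |

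One named primary would give 5%. These figures also take each test to hold its 5% level, which a trainee-level t-test on class-allocated data need not do.

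**5. What a class-level primary analysis could detect.** Inputs: 6 versus 6 courses and 15 to 25 trainees per class (Section 4.0). Assumed: two-sided 0.05, 80% power, intraclass correlation (ICC) 0.01 to 0.10, and no gain from matching. A two-sample t-test on 12 class means (10 degrees of freedom) detects 1.796 SD of a class mean. In trainee SD the detectable difference is 1.796 × √(ICC + (1 − ICC)/m), with m trainees per class:

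- m = 25, ICC 0.01: 1.796 × √0.0496 = 0.40
- m = 20, ICC 0.05: 1.796 × √0.0975 = 0.56
- m = 15, ICC 0.10: 1.796 × √0.1600 = 0.72

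**The case against.** The strongest reply is that the link exists. The t-test sentence is about the modules, the modules are said to draw on the field exercise, and Module 3 is labelled with a field evaluation. On an ordinary reading the test could include field performance. That stands: it would be wrong to infer that field performance is never assessed or that the t-test excludes it. But an implied link through one row of a table does not designate a primary outcome, and it leaves both outcome lists unchanged.

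A second reply is that material is missing. The form's opening note says data collection instruments are submitted separately, figures are not shown, and the Module 3 instrument cell is unreadable. That also stands. A reader might infer that no scoring sheet, rater or timing rule exists; the documents do not support this. A separate sheet could supply the scoring, but it would not amend the readable outcome lists or the t-test sentence.

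Third, the lists are introduced with wording that leaves them open. That is so, but an open list that omits the study's own question does not pre-specify it.

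Two further inferences should not be drawn. The plural in Section 1.0 does not show that Module 3 cannot represent the objective, because Section 8.0 itself speaks of the field exercise in the singular. Nor do the documents say that control trainees complete the VR-related scales, so that matter is a query and not a defect.

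**Conclusion.** The point holds and should be fixed before analysis. The evidence is two direct counts, 0 of 9 instruments and 0 named primary, together with a test that names no outcome. Confidence is high on the lists and on the unnamed primary. It is lower on the link between test and objective, which is loose but present.

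The 7% to 37% range should not be read as the trial's error rate. It measures multiplicity only, under an assumed significance level, number of tests and correlation. Its upper end needs nine independent tests, which is unlikely for scales completed by the same trainees. The conclusion does not depend on it.

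**What to change.** In Section 8.0:

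- Add field-exercise protocol adherence to the outcome list and name it the single primary outcome. Score it with the field evaluation already planned under Module 3, and cite the separately submitted instrument if that holds the scoring.
- State that the planned comparison applies to this outcome. Because courses are allocated, six per arm, analyse it at class level: a t-test on class means, or a model with class as a random effect.
- Make the nine listed instruments secondary or exploratory.
- Query for the sponsor: state which of the nine control trainees complete, and report any VR-specific one descriptively in the VR arm.

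Cost: if the scoring already exists, this is a change of wording. If it does not, a score must be defined and recorded in an exercise that is already required. The other scales can no longer carry the headline. Power is limited: about 0.40 to 0.72 trainee SD is detectable under the assumptions above. The ICC is left to the pilot, so this range should be recalculated once the pilot has been run.

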## 2.0 Background / Literature Review / Rationale for the study:

To successfully transfer skills and develop trainees' procedural cognitive maps VR training systems must enable full immersion into training exercises by

integrating PPE, enabling 3D object haptic interaction and natural walking to support spatial skill development, and provide trainer support (Mossel et al., 2017). Research has shown significant performance benefits from VR delivered targeted mission rehearsal (Xie et al, 2021). To realize these benefits before facing real emergencies, trainees must have the opportunity to hone their skills in a controlled setting that mimics real-life scenarios as closely as possible through fully immersive exercises (Mossel et al., 2017). This immersive context driven approach is critical for skill transfer and well understood in parallel domains (Mossel, 2020). Immersion is best achieved through a combination of sensations, including haptic (tactile touch, force feedback, temperature, etc.), audio, and visual (simulated detector reads of simulated radiation). Several recent empirical assessments of VR systems demonstrate superior skill transfer when haptic immersion is integrated in a domain appropriate way (e.g., heat exposure fire training, or stress inducing stimuli for disaster response).

It is not known whether this skill transfer occurs within the HAZMAT domain, or how to best operationalize these findings within training.

### **3.0 Inclusion and Exclusion Criteria:**

We will seek out participants who self-select to participate in the New England Consortium (TNEC) training offerings through open enrollment, including populations of any racial or ethnic background.

We will also seek out participants who are experienced trainers involved in delivering the New England Consortium (TNEC) training offerings, including trainers from any racial or ethnic background.

Participants must meet the eligibility requirements for the class. Given the class requires students to complete standardized HAZMAT training in fully suited PPE with a self-contained breathing apparatus, students must be able to speak and understand English, and not be pregnant.

The HAZWOPER certification course falls under TNEC's open enrollment courses. TNEC offers on an ongoing basis at their training center in Lowell, Massachusetts. The open enrollment courses generally consist of 15-25 students from various employers or organizations with a variety of backgrounds. Prior to each open enrollment course, TNEC trainers review the student enrollment's business types, chemical handling information and hazard exposures. Upon this review the trainers will personalize the course to best meet the needs of the attendees.

#### **Age Limits**

Min Age: 18 Years Max Age: N/A (No limit)

We will be targeting participants who participate in TNEC training offerings. Given the training takes place in Massachusetts we will use Massachusetts demographics to set our inclusion targets.

	American Indian or Alaskan Native	Asian	Black or African American	Hispanic or Latinx	Native Hawaiian or other Islander	Multiple Race, Non-Hispanic	White	Unknown
Percent	.01	9	9.9	20.5	0	0	56.7	0

## 4.0 Sample Size:

According to The New England Consortium, during the pandemic they have trained approximately 15-25 people per class once a month.

Our study follows two stages. First, we will conduct a Pilot consisting of 2 months with one month serving as a case and the other month serving as the control. The Pilot will be used to indicate effect size. (30-50 participants)

Our study will also include the main evaluation, consisting of 6 randomly selected courses that receive the IMPRINT VR intervention and 6 randomly selected control courses. (180-300 participants)

This creates a sample of approximately 300 participants.

## 5.0 Recruitment and Screening Methods:

**Recruitment process:** Given participants opt into training we will use a convenience sampling frame. Recruitment will consist of including the term, “Virtual Reality Immersive Activities”, to the existing course title and course link. The current open enrollment advertisement is available through this link: <https://tnectraining.org/training/schedule-register/>

**Screening process:** N/A

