## 6.0 Research Locations:

The evaluation will take place on site at The New England Consortium (TNEC) training center at Wannalancit Mills, as part of the University Massachusetts Lowell Campus. The facility is well equipped with the space necessary and standard equipment provided for training. The site is located at the heart of Lowell, offers shuttle bus service, state-of-the-art fiber optic cable and HVAC, and 7 elevators and 4 loading docks enabling easy access for trainees of any

background, disability status, or socioeconomic status, and has the ability to host and maintain a VR exercises for evaluation.

In addition to the Wannalancit Mills location, the evaluation will also take place at various offsite locations where TNEC has been contracted to deliver the 40-hour HAZWOPER training.

All required permissions and approvals are already obtained to conduct this research at TNEC.

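### Trainees are recruited under a virtual reality course title although half the main-evaluation courses give no VR, and the protocol does not say when they learn their allocation

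*Combined protocol and SAP*

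**What the plan says.** Section 3.0 seeks trainees who "self-select to participate in the New England Consortium (TNEC) training offerings through open enrollment". Section 5.0 calls this a convenience sample and gives the whole recruitment method in one sentence: "Recruitment will consist of including the term, “Virtual Reality Immersive Activities”, to the existing course title and course link". It names no arm and no course dates.

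Section 4.0 allocates whole courses: "6 randomly selected courses that receive the IMPRINT VR intervention and 6 randomly selected control courses". Section 8.0 describes the comparator: "In control classes, trainees will complete all of the activities following standard practice", meaning worksheets, photographs and slides. Section 6.0 adds that "the evaluation will also take place at various offsite locations where TNEC has been contracted to deliver the 40-hour HAZWOPER training", without saying whether the recruitment title applies to those classes.

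Section 11.0 has consent precede study enrolment and allows it online or in the classroom. No supplied section says when courses are randomised relative to advertising, who knows the result, or whether trainees learn their arm before or after registering and consenting.

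Against confounding, Section 8.0 says "we will use matching techniques based on trainee and trainer characteristics", and specifies: "We will use pretest matching criteria based on trainee cohort population characteristics and prior knowledge ascertained through pre-HAZWOPER training registration information".

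**The concern.** Randomising courses makes the arms comparable only if the people who join a course do not depend on its arm. It gives fair self-report comparisons only if trainees in both arms arrive with similar expectations. A recruitment title that announces VR bears on one condition or the other, depending on which courses carry it.

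The outcomes most exposed are self-reported. Section 8.0 lists the consortium's training survey and the short occupational self-efficacy scale among the outcomes, and Section 1.0 predicts a better training experience and more satisfaction with VR. Lower ratings from disappointed controls would look like that predicted benefit. The matching variables named include no measure of interest in VR or of expectations, so matching may remove only part of such a difference.

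**Working it through.** **Step 1. The plan's own figure.** Section 4.0 gives 15 to 25 trainees per class and 6 + 6 = 12 main-evaluation courses. 12 × 15 = 180 and 12 × 25 = 300, which reproduces the stated 180-300. The plan gives no power calculation, ICC or effect size to check.

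**Step 2. The two readings of Section 5.0.**

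| | Every course carries the title | Only VR courses carry the title |
|---|---|---|
| Who enrols | Same advert in both arms; balanced | Trainees can choose their arm by choosing a date |
| What controls expect | A VR title, then no VR | Standard training |
| Outcomes at risk | Satisfaction and self-efficacy ratings | Any outcome related to who enrols |
| Can a size be given? | No; the documents offer no basis | Only by assumption (Steps 3 to 5) |

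On either reading, classroom consent given after the arm is known would allow consent to differ by arm. That is a possibility only.

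**Step 3. Illustration for the VR-only reading.** Assumptions not in the documents: outcome SD 1, no true effect, ICC 0.01 to 0.10, an enrolment shift of 0.2 SD in all six VR classes, a two-sided 5% t-test on class means with 6 + 6 − 2 = 10 df, and matching not modelled. Class size m is 15 to 25 (Section 4.0).

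SE = √[2 × (ICC + (1 − ICC)/m) / 6]

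For m = 20 and ICC 0.05: SE = √[2 × (0.05 + 0.0475)/6] = √0.0325 = 0.180. The noncentrality is 0.2/0.180 = 1.11, and the noncentral t distribution gives a rejection rate of 0.171. With no shift the rate is 0.050.

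| Shift 0.2 SD | ICC 0.01 | ICC 0.05 | ICC 0.10 |
|---|---|---|---|
| m = 15 | 0.207 | 0.154 | 0.123 |
| m = 20 | 0.251 | 0.171 | 0.131 |
| m = 25 | 0.291 | 0.185 | 0.136 |

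The class-level test already allows for clustering, so a correct cluster analysis would not remove this kind of bias.

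**Step 4. If matching halves the shift.** With 0.1 SD left, m = 20 and ICC 0.05, the rate is about 8%. Over the same grid of class sizes and ICCs it runs from 7% to 11%.

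**Step 5. If some VR classes are contracted offsite classes that the advert does not reach.** Giving those classes no shift (m = 20, ICC 0.05, by simulation), the rate falls from about 17% to about 13%, 9% or 7% when 1, 2 or 3 of the six VR classes are offsite. The documents do not say how many are.

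**The case against.** The tempting stronger reading is that trainees choose their arm and course randomisation is therefore defeated. The documents do not support that as a finding. Section 5.0 refers to one existing title and one link and names no arm, which most plainly means the whole course offering. On that reading enrolment is balanced and the overall objective in Section 1.0, protocol adherence in field exercises, is not shown to be affected.

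Nor should a reader take 12% to 29%, the span of the table in Step 3, as the trial's false-positive rate. The 0.2 SD shift has no source in the documents, the figures belong to the less natural reading, and they fall once matching or unaffected offsite classes are allowed for. This objection stands in full; the figures are illustrative and do not carry the point.

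The form's opening note says that consent and recruitment materials are submitted separately. They may tell trainees that there are two versions of the course, so it would be too strong to say that controls are promised VR. This also stands. But the same note asks the protocol to describe research procedures in detail, and the order of allocation, registration and consent is trial procedure, not advert wording.

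Two further inferences are not supported. Differential consent by arm is possible under Section 11.0 but nothing shows it. Section 3.0 lets trainers personalise courses, which might suggest that content is tailored by arm; Section 8.0 commits to a common workbook and says "There will be no differences in content provided between cases and controls", so no such bias is claimed.

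What survives is that the stated recruitment rule weakens the comparison on either reading, and that the time of disclosure is missing.

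**Conclusion.** The concern holds and should be corrected before courses are advertised; it does not show that the trial is biased. On the plainer reading the risk is confined to self-reported outcomes such as satisfaction and self-efficacy, favours the intervention, and has no defensible size. On the VR-only reading the risk is selection. Under the assumptions in Step 3 the false rejection rate would be about 17%, falling to about 8% with half the shift removed by matching, or to about 13% to 7% with one to three unaffected offsite VR classes. Confidence is moderate, because the separately submitted materials have not been seen.

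**What to change.** In Section 5.0, state that all open-enrolment study courses carry one identical, truthful title and description, for example: 'Some courses include virtual reality activities; others use standard materials.' State also that each course's allocation is disclosed to trainees only after its registration has closed (for contracted offsite classes, after the roster is fixed) and after study consent has been obtained, preferably online before the course starts. Align the separately submitted recruitment and consent materials with this wording. Nothing here requires a change to course tailoring or to what trainers know.

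The cost is mainly wording. The advert becomes less promotional, and consent has to be scheduled before the first session. Some control disappointment may remain, because trainees will still know that VR was possible.
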